6.3.1.4 End of treatment assessment [Day 10 (+2 days)]

1. If the patient remains in the hospital until Day 10, the EOT will be performed at the site and all the scheduled assessments for Day 10 mentioned in [Section 6.3.1.3](#) will be performed.
2. If the patient is discharged before Day 10, the EOT can be performed either as an onsite visit or will be performed at the patient's home.

a. On-site visit:

If the patient is able to visit the hospital on Day 10, procedures for an unscheduled visit will be performed.

- COVID-19 associated symptom severity assessment
- Collection of a respiratory tract sample (nasopharyngeal swab or oropharyngeal swab or nasal aspirate or tracheobronchial aspirate or bronchial lavage) for detection (qualitative) of SARS-CoV-2 (by RT-PCR assay)*
- Partial physical examination*
- Vital signs*
- Chest X-ray*
- 12 Lead ECG*
- Clinical Laboratory assessments (haematology, serum biochemistry and urinalysis)*
- Treatment emergent AEs
- Concomitant medication*
- ICU admission status, supplemental oxygen (standard and/or high flow) and mechanical ventilation details*
- Return of empty blister packs and /or unused IMP

Study code: NV-05-983-2020
 Protocol No.: CVD-04-CD-001
 Sponsor name: [name], Limited
 Clinical Study Protocol

** Assessments may be performed at Investigator's discretion for individual patients for evaluation of patient safety or follow up of adverse events.*

OR

b. At home:

If the patient is unable to visit the hospital for the EOT, the below procedures will be performed.

- Study nurse or phlebotomist will visit the patient at his/her residence
- Blood sample collection for clinical laboratory assessments (haematology, serum biochemistry)
- A nasopharyngeal swab or oropharyngeal swab will be collected from the patient and sent for detection (qualitative) of SARS-CoV-2 RNA by RT-PCR assay based on Investigator's discretion for individual patients
- Collection of empty blister packs and /or unused IMP
- A telephonic follow up will be performed to assess the below
 - Treatment emergent AEs
 - COVID-19 associated symptom enquiry for assessment of clinical relapse
 - Concomitant medication

6.3.1.5 Visit 3: End of Study-Day 28 (+2 days) or discharge or study discontinuation whichever is earlier

- Serum Pregnancy Test (only for female patients of childbearing potential)
- Clinical Status by 10-point ordinal scale
- Clinical Status by 8-point ordinal scale
- NEWS-2 score

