- COVID-19 associated symptom severity assessment
- ICU admission status, supplemental oxygen (standard and/or high flow) and mechanical ventilation details
- Collection of a respiratory tract sample (nasopharyngeal swab or oropharyngeal swab or nasal aspirate or tracheobronchial aspirate or bronchial lavage) for detection (qualitative) of SARS-CoV-2 (by RT-PCR assay)
- Partial physical examination
- Vital signs
- Chest X-ray

Study code: NV-05-983-2020
 Protocol No.: CVD-04-CD-001
 Sponsor name: [name], Limited
 Clinical Study Protocol

- 12 Lead ECG
- Clinical Laboratory assessments (haematology, serum biochemistry and urinalysis)
- Treatment emergent AEs
- Concomitant medication

6.3.1.6 Telephonic follow up on Day 10, Day 14, Day 21 and Day 28, as applicable for the individual patient

For patients who are discharged before Day 28, a telephonic follow up assessment will be performed on Days 10 (applicable only for patients who are discharged earlier than Day 10 and if patients are unable to visit the site for EOT on Day 10), 14, 21 and 28 *as applicable for the individual patient* (window period for telephonic follow up is +2 days from scheduled day of follow up).

- Treatment emergent AEs
- COVID-19 associated symptom enquiry for assessment of clinical relapse
- Concomitant medication

6.3.1.7 Unscheduled Visit: If further assessment is found to be necessary on Telephonic Follow up

- COVID-19 associated symptom severity assessment
- Collection of a respiratory tract sample (nasopharyngeal swab or oropharyngeal swab or nasal aspirate or tracheobronchial aspirate or bronchial lavage) for detection (qualitative) of SARS-CoV-2 (by RT-PCR assay)*
- Partial physical examination*
- Vital signs*
- Chest X-ray*
- 12 Lead ECG*
- Clinical Laboratory assessments (haematology, serum biochemistry and urinalysis)*
- Treatment emergent AEs
- Concomitant medication*
- ICU admission status, supplemental oxygen (standard and/or high flow) and mechanical ventilation details*

** Assessments maybe performed at Investigator's discretion for individual patients for evaluation of patient safety or follow up of adverse events.*

Study code: NV-05-983-2020
Protocol No.: CVD-04-CD-001
Sponsor name: [name], Limited
Clinical Study Protocol

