9.5 RT-PCR (Qualitative)

Sample collection

The respiratory tract sample will be collected through nasopharyngeal swab or oropharyngeal swab or nasal aspirate or tracheobronchial aspirate (or bronchial lavage at post-baseline assessments) for the RT-PCR (qualitative) assay for SARS-CoV-2 RNA. The sample will be collected at screening, on Day 5, Day 10 and Day 28, or discharge (i.e., if the patient happens to be discharged before one or more of the mentioned timepoints, then the sample will be collected at discharge). No sample will be collected from patients at any timepoint after discharge, EXCEPT if individual patients are scheduled for an additional (unscheduled) visit, either to follow up on an AE or to report a possible 'clinical relapse' of COVID-19 or based on Investigator's discretion during the Day 10 - home visit. A sample will be collected during the unscheduled visit in such cases. The time of sample collection will be recorded.

However, the test may be performed on other days at the Principal Investigator's or a Sub-Investigator's discretion.

Testing of samples

The test will be performed at the site laboratory, if the site laboratory is not capable of performing RT-PCR assay, the testing will be conducted in an approved laboratory.

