⁹ IMPs will be administered twice daily (in the morning and evening) from Day 1 to Day 10. If the patient is discharged before Day 10, the patient will be required to continue the remainder of the IMP treatment course at home. Dosing compliance status will be checked for 10 days. Compliance will be assessed daily assessment if the patient is the hospital or based on the details in the patient diary and the empty blister packs and / unused IMP in case of patients discharged before study Day 10.

¹⁰ COVID-19 associated symptom severity assessment will be done on all days (Day 1 up to Day 28 or until discharge, whichever is earlier).

¹¹ COVID-19 associated symptom severity assessment will be done and recorded in case of patients in whom the follow up (unscheduled) visit was necessitated for reporting of clinical relapse

¹² Qualitative RT-PCR assay for detection of SARS-CoV-2 RNA in a respiratory tract sample will be performed at Screening, on Day 5, Day 10 and Day 28, or discharge (i.e., if the patient happens to be discharged before one or more of the mentioned time points, then the sample will be collected at discharge). No sample will be collected from patients at any time point after discharge, EXCEPT if individual patients are scheduled for an additional (unscheduled) visit, either to follow up on an AE or to report a possible 'clinical relapse' of COVID-19 or based on Investigator's discretion during the Day 10 - home visit. A sample for RT-PCR will be collected during the unscheduled visit in such cases.

Statistical Analysis Plan
Sponsor: [name], Inc

Study Number: NV-05-983-2020

Version: 2.0 Date: 06JAN2021

Assessments	STAGE I – Main Study ¹												Database Lock	Stage II – Extended Follow Up ²		Unscheduled Visit
	Screening ³	Randomization (Baseline) ⁴					EOT ⁵			End of Study				42	60	
Day	-3 to -1 (72 hrs)	1 (Pre-dose)	1 (Post-dose)	On all days until discharge	On all days until Day 10	4	5	7	10	14	21	28 or discharge				
Clinical Status by 10-point ordinal scale (SOLIDARITY SCALE) ¹³	•	•		•												
Clinical Status by 8-point ordinal scale ¹⁴	•	•		•												
NEWS-2 score ¹⁵	•	•		•												
Clinical Laboratory Evaluations (Hematology, Serum Biochemistry, Urinalysis)	•					•		•	•	•	•	•				•
Chest X-ray	•	•				•		•	•	•	•	•				•
12-lead ECG	•	•				•		•	•	•	•	•				•
Vital signs ¹⁶	•	•		•					•							•
Complete Physical	•															

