2. Time (no. of days) from randomization to the earliest time when ALL COVID-19 associated symptoms (fever, chills, cough, sore throat, malaise, headache, muscle pain, gastrointestinal symptoms – specifically diarrhoea and vomiting, shortness of breath or dyspnoea) are scored by the Investigator/trained study personnel as either '0=absent' or 'mild =1' in assessments over a period of 24 hours, when assessed from baseline to Day 28 or discharge from hospital (if discharge happens earlier than Day 28).

Time to ALL COVID-19 associated symptoms to become '0=absent' or 'mild =1' from Randomization = Earliest Date of ALL COVID-19 associated symptoms became either '0=absent' or 'mild =1' in assessments over a period of 24 hours – Date of randomization + 1

Time to ALL COVID-19 associated symptoms to become '0=absent' or 'mild =1' from Randomization will be summarized descriptively. Time to ALL COVID-19 associated symptoms to become '0=absent' or 'mild =1' from Randomization will be compared between the treatment groups using the Cox proportional hazard model. The hazard ratio and its corresponding two-sided 95% confidence interval (CI) and two sided *p*-value at 5% level of significance will be obtained from the above Cox proportional hazard model; Also Median time, quartile, inter quartile range estimate will be presented.

Patients whose symptom score not improved to either '0=absent' or 'mild =1 by Day 28 will be right censored as of day 28. Patients who discontinue the study for any reason – withdrawal because of an adverse event or worsening of symptoms, switch to rescue therapy, loss to follow-up, etc. – will be right censored at Day 28.

Listing will be provided for COVID-19 associated symptoms.

3. Percentage of patients with score of either '0=absent' or 'mild =1' over a period of 24 hours, for ALL COVID-19 associated symptoms by Days 4, 7, 10 14, 21 and 28 or discharge (if discharge happens earlier than one or more of the above-mentioned time points)

Statistical Analysis Plan
Sponsor: [name], Inc

Study Number: NV-05-983-2020

Version: 2.0 Date: 06JAN2021

Patients will be considered as improvement in ALL COVID-19 associated symptoms if ALL COVID-19 associated symptoms as either '0=absent' or 'mild =1'

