Patients will be considered as improvement in ALL COVID-19 associated symptoms by Days 4, 7, 10, 14, 21 and 28 will be summarized by number and percentage. Two sided Chi-square test/ Fisher-Exact (Fisher Exact test will be performed when the expected count for any cell is less than 5) test at 5% level of significance will be performed to test the difference of proportion between two treatments.

4. Time to improvement in **EACH** of the symptoms of fever, chills, cough, sore throat, malaise, headache, muscle pain, gastrointestinal symptoms- specifically diarrhoea and vomiting, shortness of breath or dyspnoea by at least 1 grade over baseline.

Note: Severity of symptoms will be evaluated once daily (preferably at or around the same clock time) on each day that the patient is admitted in the hospital. The Investigator/trained study personnel will assess (including by enquiry with the patient, as necessary) and score the severity of each COVID-19 associated symptom on a 5 point Likert-type scale (0= absent, 1= mild, 2=moderate, 3= severe, 4= very severe/critical). The improvement observed must be sustained at evaluations over a period of 24 hours, in order for this secondary efficacy endpoint to be reached.

Time to achieve symptom improvement will be considered to have been met at the earliest timepoint when the particular symptoms score has decreased by at least 1 grade over baseline.

Time to achieve symptom improvement = Date of Change from baseline value for the particular symptom score to become less than or equal to '-1' and sustained at evaluations over a period of 24 hours – Date of randomization +1

Time to achieve symptom improvement will be as follows:

Time to achieve symptom improvement will be summarized for each of the listed COVID-19 associated symptoms descriptively. Time to achieve symptom improvement of the listed COVID-19 associated symptom will be compared between the treatment groups using the Cox proportional hazard model with the baseline symptom score of each symptom as covariate and median time to achieve change from baseline as dependent variable. The hazard ratio and its corresponding two-sided 95% confidence interval (CI) and two sided *p*-value at 5% level of significance will be obtained from the above Cox proportional hazard model; Also Median time, quartile, inter quartile range estimate will be presented.

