Patients whose each symptom score does not improved by at least 1 grade over baseline up to Day 28 will be right censored as of day 28. Patients who discontinue the study for any reason – withdrawal because of an adverse event or worsening of symptoms, switch to rescue therapy, loss to follow-up, etc. – will be right censored at Day 28.

Statistical Analysis Plan
Sponsor: [name], Inc

Study Number: NV-05-983-2020

Version: 2.0 Date: 06JAN2021

5. Percentage of patients reporting a clinical relapse of COVID-19 when assessed from day of discharge to 27 days after randomization (Day 28).

Note: 'Clinical relapse' is defined as either the reappearance or worsening of severity (over the assessment on the day of discharge) of one or more of the above-mentioned COVID-19 associated symptoms, or the appearance of any of the symptoms (due to COVID 19 infection) for the first time after discharge. This endpoint will be assessed only for those patients that were discharged before Day 28.

Patients reporting a clinical relapse of COVID-19 will be summarized by number and percentage. Two-sided Chi-square test/ Fisher-Exact test at 5% level of significance will be performed to test the difference of proportion between two treatments with two-sided 95% level of significance.

6. Time (no. of days) to negative conversion of detectable SARS-CoV 2 viral RNA in the RT-PCR assays of respiratory sample, from randomization.

Time to negative conversion will be compared between the treatment groups using the Cox proportional hazard model with cycle threshold value (RdRp Target) at baseline as covariate. The hazard ratio and its corresponding two-sided 95% confidence interval (CI) and two sided p -value at 5% level of significance will be obtained from the above Cox proportional hazard model; Also Median time, Quartile, Inter quartile range estimate will be presented and Kaplan-Meier plot will be plotted. Patients who don't turn to be SARS-CoV-2 negative by Day 28 will be right-censored as of day 28. Patients who discontinue the study for any reason – withdrawal because of an adverse event or worsening of symptoms, switch to rescue therapy, loss to follow-up, etc. – will be right censored at Day 28.

Listing will be provided for RT-PCR.

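### Secondary endpoints 2, 4 and 6 do not name discharge, so discharged patients without the event are carried to Day 28 as event-free; endpoint 15 stops counting deaths at discharge

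*SAP*

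**What the plan says.** **Censoring.** In SAP 10.6.2, endpoint 6 (time to negative PCR) censors at Day 28 the patients who do not "turn to be SARS-CoV-2 negative by Day 28 will be right-censored as of day 28". Endpoint 2 (all symptoms absent or mild) says the same of patients without the event "by Day 28 will be right censored as of day 28", and endpoint 4 (improvement of each symptom) has an equivalent sentence. A second sentence under each sends discontinuations for any reason to Day 28. Neither sentence mentions discharge.

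**Measurement.** Protocol 9.5: "No sample will be collected from patients at any timepoint after discharge, EXCEPT if individual patients are scheduled for an additional (unscheduled) visit", or a swab is taken at the investigator's discretion at the Day 10 home visit. SAP Table 1, footnote 10: "COVID-19 associated symptom severity assessment will be done on all days (Day 1 up to Day 28 or until discharge, whichever is earlier". The note to endpoint 4 has symptoms scored "on each day that the patient is admitted in the hospital".

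The exceptions after discharge are:
- unscheduled visits, where symptoms are scored for "patients in whom the follow up (unscheduled) visit was necessitated for reporting of clinical relapse" (SAP Table 1, footnote 11) and a PCR sample is taken (footnote 12);
- the on-site Day 10 visit after earlier discharge: "If the patient is able to visit the hospital on Day 10, procedures for an unscheduled visit will be performed" (Protocol 6.3.1.4), with symptom severity listed and PCR optional;
- the discretionary Day 10 home swab, and extra PCR at the investigator's discretion (Protocol 9.5).

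Telephone calls cover only "COVID-19 associated symptom enquiry for assessment of clinical relapse" (Protocol 6.3.1.4 and 6.3.1.6).

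**Deaths.** Endpoint 15 counts deaths from randomization to Day 28 or discharge, whichever is earlier, in both documents. Part c of the primary endpoint requires survival through Day 28, and Protocol 6.3.1.6 plans a Day 28 call for discharged patients.

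**The concern.** A right-censoring time asserts that the patient was observed without the event up to that time. For a patient discharged PCR-positive on Day 8, the Day 28 rule normally makes that assertion for 20 days without a sample. The arm that empties its beds faster collects more of these patients, so its recorded event rate falls even if the drug does nothing to virus or symptoms. Time to discharge is itself secondary endpoint 1, so a difference between the arms is something the trial is looking for. A drug that speeds discharge would tend to look worse on viral clearance and symptom improvement; one that delays discharge would tend to look better.

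For endpoint 15, the Stage I mortality comparison omits deaths that the trial must already ascertain for its primary endpoint. The guidance appended to the protocol (Appendix I, non-binding) asks for time points in days after randomization and for vital status on all subjects.

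**Working it through.** **The plan's figures.** The documents give no discharge or conversion rates, so there is no planned figure to reproduce here. The one design figure, 631 events for the primary endpoint, reproduces as 4 × (1.960 + 0.842)² / (ln 1.25)² ≈ 631 and is not touched by this point.

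**Closed-form check, endpoint 6.** Assumptions: no virological effect; exponential conversion with mean 14 days; exponential discharge with control median Day 10; a swab at discharge and none later.
- Conversion rate λ = 1/14 = 0.0714 per day.
- Control discharge rate μ = ln 2 / 10 = 0.0693; at a discharge hazard ratio of 1.25, 0.0866.
- Proportion with a recorded negative by Day 28 = λ/(λ+μ) × (1 − e^(−28(λ+μ))).
- Control: 0.0714/0.1407 × (1 − e^(−3.94)) = 49.8%. Favipiravir: 0.0714/0.1581 × (1 − e^(−4.43)) = 44.6%.
- Control patients discharged without a negative: 0.0693/0.1407 × 0.981 = 48.3%.

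A drug with no effect on virus therefore shows about 5 percentage points fewer recorded conversions by Day 28.

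**Simulation, endpoint 6.** Settings: 100,000 to 150,000 patients per arm; PCR on Days 5, 10 and 28 or at discharge; none to all of those discharged before Day 10 swabbed on Day 10; exponential or Weibull discharge; with or without a shared frailty linking recovery and discharge; Cox model under the Day 28 rule; no true effect.

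| Setting | Discharge HR 1.25 | Discharge HR 1.5 |
|---|---|---|
| No one waits for a negative PCR, all runs | 0.89 to 0.98 | 0.81 to 0.97 |
| of which one set, exponential discharge | 0.90 to 0.96 | 0.82 to 0.93 |
| of which one set, Weibull shape 3 | 0.96 to 0.98 | 0.92 to 0.96 |
| Half leave only after a negative PCR | 0.96 to 1.00 | 0.94 to 1.00 |
| All leave only after a negative PCR | 1.00 to 1.04 | 1.01 to 1.06 |

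With equal discharge the result is 0.99 to 1.01.

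**Alternatives under no effect.** Cox censored at the last sample drifts up to about 1.10: the discharge swab comes earlier in the faster arm, so conversions are detected earlier there. An interval-censored proportional hazards model stays at about 0.96 to 1.03.

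**Endpoint 15.** Assume Day 28 mortality of 5% to 10%, with 10% to 20% of deaths after discharge. Deaths left out per arm: 390 × 0.05 × 0.10 = 2.0, up to 390 × 0.10 × 0.20 = 7.8.

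**Where later deaths do appear.** They enter the worst-rank sensitivity analysis (SAP 10.6.1), the adverse-event tables (SAP 10.7.1) and Stage II item 2b to Day 60, whose analysis sentence names only disease worsening. The interim mortality comparison (SAP Appendix I) is exploratory. None of these is a final comparison of deaths alone through Day 28.

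**The case against.** **A rule does exist.** A reader might infer that discharged patients have no censoring rule. They do: the Day 28 sentence covers them by default. The gap is that discharge is unnamed and the default runs past the last measurement.

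**Day 28 carrying can be deliberate.** Keeping discharged patients at risk is a recognised competing-event treatment. This stands for endpoint 2, which is defined only to Day 28 or discharge, although the SAP does not say that in-hospital recovery is the target. It does not carry over to endpoints 4 and 6, whose definitions are not limited to the stay.

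**The bias is conditional and often conservative.** This stands. It vanishes with equal discharge and shrinks, or reverses slightly, if sites wait for a negative PCR; Protocol 6.1.4 leaves discharge to national rules or hospital practice. The low ends of the ranges need exponential discharge, which sends some oxygen-dependent patients home within days.

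**Discharge depends on recovery, so earlier censoring is informative too.** This also stands, and it is why plain recensoring is not enough for endpoint 6.

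**Later deaths are used elsewhere.** True. A reader might infer that the trial ignores deaths after discharge; the documents do not support that. Only endpoint 15 excludes them.

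**Conclusion.** The point holds for secondary endpoints and should be fixed. For endpoints 4 and 6, a difference in discharge timing biases the hazard ratio even with no effect on symptoms or virus, mostly against the arm discharged sooner. For endpoint 6 under no effect, the size is about 0.89 to 0.98 at a discharge hazard ratio of 1.25 and 0.81 to 0.97 at 1.5. That rests on assumed mean conversion of 14 days, control median discharge on Day 10 and no one waiting for a negative PCR. No size is claimed for endpoint 4. For endpoint 2 the fault is an unstated target, not a demonstrated bias. Endpoint 15 leaves out perhaps 2 to 8 deaths per arm of 390, again on assumed rates.

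Two stronger readings are not supported. The primary analysis is not affected, because there discharge after reaching a score of 4 helps complete the event (SAP 10.6.1, part b). Nor does this show a false-positive risk in favour of favipiravir: the direction depends on which arm leaves hospital sooner, and no error rate was estimated.

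**What to change.** 1. **Endpoint 15:** count all deaths from randomization through Day 28 in all ITT patients regardless of discharge, using the Day 28 contact already planned, and report the number with unknown vital status.
2. **Endpoint 6:** use an interval-censored proportional hazards model (last positive to first negative sample), keeping the baseline cycle-threshold covariate. Right-censor patients discharged without a negative result at their last sample, including any taken after discharge.
3. **Endpoint 4:** censor patients discharged without the event at their last recorded score.
4. **Endpoint 2:** do the same, or state that the target is in-hospital recovery with discharge as a competing event.

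For items 2 to 4, keep Day 28 censoring for deaths and for discontinuations due to treatment-related adverse events or lack of efficacy, as SAP 10.6.1 does for the primary endpoint. Report the present Day 28 rule as a sensitivity analysis.

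**Cost:** item 1 needs only wording. The rest is wording and modest programming, mostly for the interval-censored model. Fewer patients remain at risk at late days, and discharge may still be informative.
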